2.3.3. Clinical laboratory evaluation

Not Applicable.

2.3.4. Vital signs, physical findings and other observations related to safety

Not Applicable.

2.3.5. Concomitant medications and procedures

Patient's concomitant medications will be coded using the ATC WHO Drug dictionary latest version in force at the date of database lock.

Patient's concomitant procedures will be coded using the MedDRA dictionary latest version in force at the date of the database lock.

CONFIDENTIAL	STATISTICAL ANALYSIS PLAN N° GDX-44-016 VERSION N° 4.0 (REF I011622)	F015830-03 Page 12 / 35
--------------	--	----------------------------

3. STATISTICAL METHODS

3.1. General considerations

After the database lock, the statistical analysis will be performed by a CRO Biostatistician on the basis of the present document.

A quality control of the statistical analysis will be performed to ensure the reliability of the results.

Thorough description of all parameters reported will be presented separately by arm. Summary tabulated results will be provided by arm and assessment time, if relevant, or they will be replaced by the corresponding individual data listings if too few subjects are concerned.

Tabulations of quantitative parameters will include the following summary statistics: Number of Patients / Mean / Standard Deviation (SD) / Minimum / Median / Maximum. The mean and median will be reported to 1 decimal more than the data; SD to 2 more decimals than the data; and minimum and maximum to the same number of decimals as the data.

Rules for rounding decimals (example= the weight):

If decimal is <0.5 then round the number down (example: 65.3kg is rounded to 65kg)

If decimal is ≥ 0.5 then round the number up (example: 65.6kg is rounded to 66kg)

Tabulations of frequencies for categorical data will include all possible categories and will display the number of observations in a category as well as the percentage (%) relative to the respective arm. Percentages will be rounded to one decimal place.

The baseline value will be defined as the last available value prior to administration of the investigational product.

All statistical tests will be performed at the significant threshold of 2.5% one sided (5% two-sided).

SAS® Version 9.4 (or later version) will be used for all descriptive summaries and inferential analyses.

3.2. Null and alternative hypothesis

Statistical hypotheses

From a clinical perspective, a 12% non-inferiority margin was not considered importantly different on diagnostic quality of contrast agents, therefore it is relevant to establish acceptable diagnostic quality of Elucirem® relative to Dotarem®.

The statistical hypotheses are the followings:

- H0: $p_{(\text{excellent+good for Elucirem}^{\text{®}})} - p_{(\text{excellent+good for Dotarem}^{\text{®}})} \leq - 0.12$

- H1: $p_{(\text{excellent+good for Elucirem}^{\text{®}})} - p_{(\text{excellent+good for Dotarem}^{\text{®}})} > - 0.12$

Non-inferiority will be evaluated by testing whether the lower bound of the two-sided Confidence Interval (CI) for the difference of “Elucirem®– Dotarem®”, in proportion of patients presenting with images of excellent and good diagnostic quality according to off-site readers, excludes a 12% difference.

In case of conclusion of non-inferiority of Elucirem® compared to Dotarem®, the superiority of Elucirem® compared to Dotarem® will then be tested in the same way as described above for the non-inferiority (lower bound of the CI is above 0).. No adjustment for multiplicity is needed as it is a simple closed testing procedure.

CONFIDENTIAL	STATISTICAL ANALYSIS PLAN N° GDX-44-016 VERSION N° 4.0 (REF I011622)	F015830-03 Page 13 / 35
--------------	--	----------------------------

3.3. Determination of sample size

Sample sizes of 62 in each arm achieve 80% power to detect a difference of 0 when the non-inferiority difference is -0.12. In the reference arm (Dotarem®), the proportion of patients presenting with CBV map of excellent and good diagnostic quality is 94% [1]. In the Elucirem® arm, this proportion is assumed to be 82% under the null hypothesis. The power was computed for the case when the actual treatment arm proportion is 94%. The statistical test used is the one-sided Z test (unpooled). The significance level of the test is 2.5% (unilateral, 5% bilateral).

Assuming a 10% drop-out rate, the sample size increases to 138 patients to test that the proportion of patients presenting with images of excellent and good quality in the Elucirem® arm is not inferior to the proportion of patients presenting with images of excellent and good quality in the Dotarem® arm.

The sample size was calculated using the PASS statistical software by Exystat.

3.4. Adjustment for covariates

Not Applicable.

3.5. Handling of dropouts or missing data

Not Applicable.

3.6. Interim analyses and data monitoring

No interim analysis is planned.

3.7. Multicenter studies

As the primary criterion is evaluated by off-site-readers, the site effect will not be included in the primary analyses.

3.8. Multiple comparisons/Multiplicity

Multiple testing regarding secondary criteria (quantification of rCBV) will be taken into account by using the Benjamini-Hochberg method.

The adjusted p-values according to the Benjamini-Hochberg procedure will be calculated as follows:

$$p \text{ Benjamini-Hochberg} = \min (p \times nbp / j, 1)$$

where:

- p is the original p-value (without adjustment),
- nbp is the number of calculated p-values (i.e., the number of comparisons),
- j is the rank of the original p-value when all p-values are ranked in ascending order.

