The number of patients included in each site will be displayed in a disposition table overall and by arm.

11.4.5 *Multiple Comparisons/Multiplicity*

For this trial, there will be one interim efficacy analysis, which will be conducted after 50% of the patients will be assessed, by off-site readers, in terms of diagnostic quality of images. As an interim analysis of the primary endpoint is planned, an adjustment of the Type I error will be performed. The interim analysis will be performed at a significant level of 0.001 (unilateral, 0,002 bilateral). The final analysis will be performed at a significant level of 0.024 (unilateral, 0.048 bilateral).

When considering the testing of the superiority of Elucirem® compared to Dotarem® (after non-inferiority was demonstrated), no adjustment for multiplicity is needed as it is a simple closed testing procedure.

Regarding the quantification of rCBV for differentiating tumor grade, the Benjamini-Hochberg method will be used to account for multiple testing.

| | | |
|--|--|----------------------------|
|  CONFIDENTIAL | Protocol No. GDX-44-016 Version No. 1.0 - ITA Date 15 March 2023 | F015919-05 Page 52 / 59 |
|--|--|----------------------------|

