The Mann-Whitney U-test will be used to test the difference in rCBV between the two trial arms by tumor grade categorization (low and high grade) and between patients with high-grade and low-grade gliomas, within each of the two study arms at the significant level of 5%. The analysis will be performed for off-site assessment and presented for each off-site reader and overall (taking into account the consensus decision).

If more than one lesion were detected by a reader, the maximum value for rCBV will be considered for the analysis at reader level. For the overall rCBV analysis taking into account the consensus decision, the maximum value for rCBV of consensus reading will be considered. If no consensus was needed, the maximum value for rCBV between the two off-site readers will be considered.

Two analyses will be performed. The first one will consider the gliomas' grade categorization (high-grade versus low-grade) according to the stratification factor used at randomization, the second one will use the tumor grade categorization as per histopathological results (if any) collected during the study.

Categorization as per histopathological results will be the following:

- Grade 1 and Grade 2 = Low grade,
- Grade 3 and Grade 4 = High grade.

The Benjamini-Hochberg method will be used to account for multiple testing for the two analyses separately.

Grade per categorization (high-grade versus low-grade) according to the stratification factor used at randomization will be cross tabulated with the categorization of the grade as per off-site reader assessment, by treatment arm.

If more than one lesion were detected by a reader, the worst grade according to rCBV will be considered. Then, for the overall analysis of grade according to rCBV taking into account the consensus decision, the worst grade according to rCBV of consensus reading will be considered. If no consensus was needed, the worst grade according to rCBV between the two off-site readers will be considered. Moreover, for patients with histopathological results, categorization of the grade per histopathology will be cross tabulated with the categorization of the grade as per off-site reader assessment, by treatment arm.

Categorization as per off-site reader assessment will be the following (according to the Imaging Charter V1.0):

- $rCBV < 1.75$ = Low grade,
- $rCBV \geq 1.75$ = High grade.

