Table 14.2.2.16 rCBV by treatment arm assigned at randomization and by grade (stratification variable at randomization) – Comparison within arms – Off-site PPS

Table 14.2.2.17 rCBV by treatment arm assigned at randomization and by grade (stratification variable at randomization) – Comparison between arms – Off-site FAS

Table 14.2.2.18 rCBV by treatment arm assigned at randomization and by grade (stratification variable at randomization) – Comparison within arms – Off-site FAS

Table 14.2.2.19 rCBV by treatment arm assigned at randomization and by grade (according to histopathology) – Comparison between arms – Off-site PPS - Patients With a Detected Lesion Matching Histopathology

Table 14.2.2.20 rCBV by treatment arm assigned at randomization and by grade (according to histopathology) – Comparison within arms – Off-site PPS - Patients With a Detected Lesion Matching Histopathology

Table 14.2.2.21 rCBV by treatment arm assigned at randomization and by grade (according to histopathology) – Comparison between arms – Off-site FAS - Patients With a Detected Lesion Matching Histopathology

Table 14.2.2.22 rCBV by treatment arm assigned at randomization and by grade (according to histopathology) – Comparison within arms – Off-site FAS - Patients With a Detected Lesion Matching Histopathology

Table 14.2.2.23 Grade assessed by off-site readers (based on rCBV) by treatment arm assigned at randomization and by grade (stratification variable at randomization) – Off-site PPS

Table 14.2.2.24 Grade assessed by off-site readers (based on rCBV) by treatment arm assigned at randomization and by grade (stratification variable at randomization) – Off-site FAS

CONFIDENTIAL	STATISTICAL ANALYSIS PLAN N° GDX-44-016 VERSION N° 4.0 (REF I011622)	F015830-03 Page 32 / 35
--------------	--	----------------------------

Table 14.2.2.25 Grade assessed by off-site readers (based on rCBV) by treatment arm assigned at randomization and by grade (according to histopathology) – Off-site PPS - Patients With a Detected Lesion Matching Histopathology

Table 14.2.2.26 Grade assessed by off-site readers (based on rCBV) by treatment arm assigned at randomization and by grade (according to histopathology) – Off-site FAS - Patients With a Detected Lesion Matching Histopathology

Table 14.2.2.27 Reliability of the T2* signal intensity time curve for diagnosis and level of diagnosis confidence by treatment arm assigned at randomization at Lesion Level – Off-site PPS

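### The Benjamini-Hochberg formula in SAP 3.8 leaves out the step-up minimum, so read literally it can lose a secondary rCBV rejection and reverse the order of significance.

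*SAP*

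**What the plan says.** SAP 3.8 sets the rule: "Multiple testing regarding secondary criteria (quantification of rCBV) will be taken into account by using the Benjamini-Hochberg method". It continues "The adjusted p-values according to the Benjamini-Hochberg procedure will be calculated as follows" and gives the expression min(p × nbp / j, 1). Here p is the unadjusted p-value, "j is the rank of the original p-value when all p-values are ranked in ascending order", and "nbp is the number of calculated p-values (i.e., the number of comparisons").

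SAP 5.5.3 describes the tests. Mann-Whitney tests at the 5% level compare rCBV between arms in each grade category, and between high and low grade within each arm. Results are "presented for each off-site reader and overall (taking into account the consensus decision"). This is done once with the stratification grade and once with the histopathological grade, and "The Benjamini-Hochberg method will be used to account for multiple testing for the two analyses separately".

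The protocol names the method without a formula: "the Benjamini-Hochberg method will be used to account for multiple testing" (sections 11.3.6.2 and 11.4.5).

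**The concern.** The only minimum in the SAP expression is the cap at 1. BH is a step-up procedure: a hypothesis is rejected if its own p-value, or any larger one, meets its rank-specific threshold. An adjusted p-value has to carry that through a minimum over the higher ranks. Without it, the SAP names one procedure and writes down another.

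At stake are the rCBV comparisons only. A lost between-arm rejection would hide an rCBV difference between the two products. A lost within-arm rejection would understate grade differentiation, which is a named secondary objective. A table that calls p = 0.04 significant and p = 0.03 not significant would also be hard to defend in the study report.

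A smaller gap sits beside this one. nbp depends on which tests are counted together, and the SAP settles that only in part.

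**Working it through.** The SAP gives a formula and no numerical result here, so there is no figure to reproduce. The check sets the formula against standard BH.

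**Inputs.** Formula, j and nbp: SAP 3.8. Level 0.05: SAP 5.5.3. Family size and effect sizes are assumptions, because the documents give neither.

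**Formulas.** With m = nbp and p(1) ≤ … ≤ p(m):
- SAP: a(j) = min(m × p(j) / j, 1)
- BH: b(j) = min over k ≥ j of min(m × p(k) / k, 1)

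**What follows directly.** The term k = j is one of those minimised in b(j), so b(j) ≤ a(j) always, and the SAP formula cannot reject anything that BH does not. The two differ only if p(k)/k < p(j)/j for some k > j. The largest rank that BH rejects meets its own threshold and is therefore also rejected by the SAP formula. So the two never disagree on whether anything is rejected, and every lost rejection has a smaller raw p-value than one still called significant.

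**Worked examples** (BH values checked against a standard software routine):

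| Raw p | SAP formula | BH |
|---|---|---|
| 0.03, 0.04 | 0.06, 0.04 | 0.04, 0.04 |
| 0.001, 0.030, 0.035, 0.600 | 0.004, 0.060, 0.047, 0.600 | 0.004, 0.047, 0.047, 0.600 |
| 0.030, 0.035, 0.040, 0.045 | 0.120, 0.070, 0.053, 0.045 | 0.045 for all four |
| 0.01, 0.02, 0.03, 0.04 | 0.04 for all four | 0.04 for all four |

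In the second row, for example, rank 2 gives 0.030 × 4 / 2 = 0.060 and rank 3 gives 0.035 × 4 / 3 = 0.047. BH carries the 0.047 down to rank 2, so the SAP formula loses that test. In the third row the SAP formula keeps only the largest raw p-value and BH rejects all four. The fourth row shows that many patterns are unaffected.

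**How often.** Share of simulated families in which at least one 5% decision is lost (400,000 families per scenario, independent two-sided z tests):

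| Tests | Equal effects in all tests, mean z = 0 / 1 / 2 / 3 | Effects in half the tests, mean z = 2 / 3 / 4 / 5 |
|---|---|---|
| 2 | 0.06 / 0.39 / 1.27 / 0.57% | 0.28 / 0.18 / 0.05 / 0.01% |
| 4 | 0.09 / 0.95 / 3.56 / 1.01% | 1.35 / 1.01 / 0.14 / 0.02% |
| 12 | 0.11 / 2.41 / 8.99 / 0.94% | 5.19 / 2.11 / 0.18 / 0.03% |

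No scenario produced an extra rejection.

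**Family size.** Per grade definition there are 2 between-arm and 2 within-arm tests, so 2 + 2 = 4 if taken together, or 2 if kept apart. The table list in SAP 6.1 puts them in separate tables (14.2.2.15 to 14.2.2.22). Pooling reader 1, reader 2 and overall gives 4 × 3 = 12. The same tables are repeated for the Off-site PPS and the Off-site FAS, so counting every calculated p-value gives 12 × 2 = 24. The choice matters under any formula. If the smallest raw p-value is 0.01 and no higher rank gives a lower value, the adjusted value is 0.02 with 2 tests, 0.04 with 4 and 0.12 with 12.

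**The case against.** The best defence is that the SAP names the right method throughout. It specifies SAS, and a programmer who uses a standard BH routine gets correct values. The defect then lies in the written formula under a correctly named method. The error is also conservative, and the rCBV tests gate no other test.

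Most of that stands, and it limits the weight of the point. It does not remove it. SAP 3.1 has a CRO biostatistician perform the analysis on the basis of the SAP. If the CRO codes the formula, adjusted p-values can be wrong. If it uses a standard routine, the output can differ from the written plan.

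A second objection concerns size. The 3.6% and 9.0% peaks need a mean z of 2 in every test, including the between-arm ones, whereas the trial expects the products to perform alike. The four tests are also not independent, because they are contrasts of the same four arm-by-grade cells. A simulation of that structure with no arm difference (1,000,000 runs; assumed normal means, with 31 patients per cell or a 20/42 low/high split) lost a decision in about 0.3, 0.5, 1.2, 0.9, 0.2 and 0.04% of runs at within-arm mean z of 0, 1, 2, 3, 4 and 5. This is fair: for four tests, about 1% is a more realistic peak than 3.6%. It agrees with the half-effects column above, where the four-test maximum is 1.35%. Under the complete null, the dependent figure is higher than the independent one (0.09%).

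**Conclusion.** The point holds. The formula in SAP 3.8, followed literally, does not give BH adjusted p-values, and nothing elsewhere in the SAP or protocol corrects it. It can lose a rejection, misreport adjusted p-values, and call a larger raw p-value significant while a smaller one is not. It cannot inflate false discoveries.

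The formula error and the order reversal follow from the algebra and rest on no assumption. The frequencies do rest on assumptions: family size, effect sizes and, in the main simulation, independence. Results from two readers of the same patients would be correlated, so the 12-test figures are only indicative. A lost decision is uncommon in most scenarios. Given the limited reach, this should be corrected before analysis but does not threaten the trial's main conclusion. The undefined nbp is missing detail, secondary to the formula error.

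**What to change.** In SAP 3.8, replace the expression by p_BH(j) = min over k ≥ j of min(1, nbp × p(k) / k), or state that adjusted p-values come from a standard BH/FDR routine.

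In the same edit, add a sentence listing the tests that make up nbp in each of the two grade analyses. It should say whether between-arm and within-arm tests form one family, whether the reader 1, reader 2 and overall results are pooled, and whether the PPS and FAS are adjusted separately. Four tests per grade definition is one natural reading. The choice should be fixed before results are seen.

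The cost is one line and one sentence. No data collection, design or clinical procedure changes, and standard software already implements the corrected formula.

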3.9. Use of an “efficacy subset” of subjects

As the primary objective is to demonstrate non-inferiority of Elucirem® compared to Dotarem®, the corresponding analysis will be done using the PPS and then will be repeated using the FAS.

CONFIDENTIAL	STATISTICAL ANALYSIS PLAN N° GDX-44-016 VERSION N° 4.0 DATED: DECEMBER 20, 2024 (REF I011622)	F015830-03 Page 14 / 35
--------------	--	----------------------------

3.10. Active control studies intended to show equivalence

Not Applicable.

3.11. Examinations of subgroups

Not Applicable.

CONFIDENTIAL	STATISTICAL ANALYSIS PLAN N° GDX-44-016 VERSION N° 4.0 (REF I011622)	F015830-03 Page 15 / 35
--------------	--	----------------------------

4. CHANGES IN THE CONDUCT OF THE STUDY OR PLANNED ANALYSES

An interim analysis (IA) on the primary evaluation criterion was planned to be performed when 50% of the patients are assessed by the off-site readers, in terms of diagnostic quality of images.

Based on this analysis, an internal committee had the possibility to decide to early terminate the trial if the lower bound of the two-sided 99.8% CI was above the pre-stated margin of noninferiority (-12%) as Elucirem® would be declared non-inferior to Dotarem® for efficacy.

Due to unanticipated concomitance of recruitment pace and biometry operations, the result of the IA would have been available only when all patients would have been included and treated and so would not have had any impact on the recruitment and the study. Therefore, it was decided to not perform the IA in June 2024.

As only one analysis is done, there is no need to adjust the Type I error. Therefore, the final analysis will be performed at a significant level of 0.025 (unilateral, 0.05 bilateral) leading to the construction of a two-sided 95% CI for the non-inferiority testing.

CONFIDENTIAL	STATISTICAL ANALYSIS PLAN N° GDX-44-016 VERSION N° 4.0 (REF I011622)	F015830-03 Page 16 / 35
--------------	--	----------------------------

5. STATISTICAL AND ANALYTICAL PLANS

5.1. Disposition of subjects

Patient disposition will be based on all patients who have signed their ICF and tabulated, by arm and overall for the following categories:

- Number (percentage) of patients in each Data Set,
- Number (percentage) of patients overall disposition,
- Number (percentage) of patients by trial visit,
- Number (percentage) of patients by country and center,
- Number (percentage) of patients screen failed (only overall) and prematurely discontinued from the trial,
- Reason for screen failure (only overall) and premature discontinuation.

5.2. Data Sets Analysed and protocol deviations

Data sets analysed

The patient sets for this trial, will be presented by arm and overall, and are defined below:

- Screened Patients Set (SPS) will include all patients having signed the ICF,
- All Randomized Patients Set (ARPS) will include all patients having signed the inform consent form and randomized according to the assigned treatment arm,
- All Randomized and Treated Patients Set (ARTPS) will include all patients having signed the inform consent form, randomized according to the assigned treatment arm and treated in the trial,
- Full Analysis Set (FAS) will include all patients who have a valid primary criterion assessment, that is to say images available, with a perfusion CBV map considered as technically adequate (i.e., poor fair, good) and read. Patients will be analysed according to the treatment arm assigned at randomization. Two FAS will be considered in this study:
 - Off-site FAS taking into account off-site assessments for the two off-site readers,
 - On-site FAS: taking into account on-site assessments.
- Per-Protocol Set (PPS) will include all patients from the FAS who have no major protocol deviations and who have complied with the treatment allocated at randomization. Two PPS will be considered in this study:
 - Off-site PPS: all patients from the Off-site FAS and without major protocol deviations for both assessments and specific to the off-site assessment,
 - On-site PPS: all patients from the On-site FAS and without major protocol deviations for both assessments and specific to the on-site assessment,
- Safety Set (SS) will include all patients having received at least one injection of IMP regardless of the quantity. Patients will be analysed according to the treatment really received.

CONFIDENTIAL	STATISTICAL ANALYSIS PLAN N° GDX-44-016 VERSION N° 4.0 (REF I011622)	DATED: DECEMBER 20, 2024	F015830-03 Page 17 / 35
--------------	--	--------------------------	----------------------------

Table 2: Datasets analysed

	Screened Patient Set (SPS)	Safety Set (SS)	Full Analysis Set (FAS)		Per Protocol Set (PPS)	
			Off-site FAS	On-site FAS	Off-site PPS	On-site PPS
Disposition	✓					
Protocol Deviation	✓					
Population characteristics at baseline			✓		✓	
Exposure		✓				
Efficacy: Primary criterion			✓		✓	
Efficacy: Secondary criteria			✓	✓	✓	✓
Safety		✓				
Data Listings	✓					

Protocol deviations

As per ICH E3 guideline, a protocol deviation is any change, divergence, or departure from the study design or procedures defined in the protocol, with or without impact to the patient safety or the efficacy assessments. Protocol deviations are displayed in the Clinical Study Report (CSR) as a metric of the feasibility and reliability of the study. The list of protocol deviations is presented in the table below and can be updated, if necessary, before locking the database. Protocol deviations will be gathered from monitoring files, clinical database, IWRS database and external vendors of off-site data (Imaging).

Protocol deviations will be categorized into major and non-major deviations. A major deviation is defined as a deviation having **an impact on the primary criterion** (diagnostic quality of the CBV map generated according to off-site readers) and an impact on the secondary criterion regarding the diagnostic quality of the CBV map generated according to on-site readers. A first categorisation is done in this document, then categorisation will be reviewed before database lock, during the statistical Data Review Meeting (DRM). The decision will be duly described in the meeting minutes.

The deviations are listed in the table below:

Table 3: Listing of protocol deviations

Categorisation of the deviation	Protocol Deviation Coded Term	Source	Status
Inclusion criteria not met	Patient having not reached legal majority age	Clinical Database	Non major for both assessments
	Patient not presenting, at the time of inclusion, naïve or recurrent primary glial tumor and/or tumor grade are not available in patients' medical records	Clinical Database	Major for both assessments
	Patient having not signed the ICF	Clinical Database	Major for both assessments

CONFIDENTIAL	STATISTICAL ANALYSIS PLAN N° GDX-44-016 VERSION N° 4.0 (REF I011622)	F015830-03 Page 18 / 35
--------------	--	----------------------------

Categorisation of the deviation	Protocol Deviation Coded Term	Source	Status
	Patient not affiliated to national health insurance according to local regulatory requirements	Clinical Database	Non major for both assessments
Non-inclusion criteria met	Patient with known contraindication(s) to the use or with known sensitivity to one of the products under investigation or to other GBCAs (such as hypersensitivity, post-contrast acute kidney injury)	Clinical Database	Non major for both assessments
	Patient presenting with any contraindication to MRI examinations	Clinical Database	Non major for both assessments
	Post treatment patient presenting with pseudo-progression instead of tumor recurrence	Clinical Database	Major for both assessments
	Patient presenting with severe renal insufficiency, defined as an estimated Glomerular Filtration Rate (eGFR) < 30 mL/min/1.73 m ² assessed within 1 day prior to contrast agent injection	Clinical Database	Non major for both assessments
	Patient having received any contrast agent (MRI or CT) within 3 days prior to IMPs administration or scheduled to receive any contrast agent within 24 hours after IMP administration	Clinical Database and monitoring	Major for both assessments for the first part of the criterium Non major for both assessments for the second part of the criterium
	Pregnant female patient (a female patient of childbearing potential or with amenorrhea for less than 12 months must have a negative pregnancy test within 1 day prior to trial MRI and must be using medically approved contraception method until the last trial visit)	Clinical Database	Non major for both assessments
	Patient having received any investigational medicinal product within 7 days prior to trial entry or scheduled to	Clinical Database	Non major for both assessments

CONFIDENTIAL	STATISTICAL ANALYSIS PLAN N° GDX-44-016 VERSION N° 4.0 (REF I011622)	F015830-03 Page 19 / 35
--------------	--	----------------------------

Categorisation of the deviation	Protocol Deviation Coded Term	Source	Status
	receive any investigational treatment in the course of the trial		
	Patient previously randomized in this trial	Clinical Database	Major for both assessments
	Patient with anticipated, current or past condition (medical, psychological, social or geographical) that would compromise the patient's safety or her/his ability to participate in the trial	Clinical Database	Non major for both assessments
	Patient unlikely to comply with the protocol, e.g., uncooperative attitude, inability to return for follow-up visits and/or unlikelihood of completing the trial	Clinical Database	Non major for both assessments
	Patient related to the investigator or any other trial staff or relative directly involved in the trial conduct	Clinical Database	Non major for both assessments
Imaging	Imaging acquisitions guidelines not respected with major impact on the primary criterion / Image technically not adequate at V2 according to off-site reader	Imaging QC (external vendors off site data)	Major for Off-site assessment
	Imaging acquisitions guidelines not respected with non-major impact on the primary criterion or on secondary criteria	Imaging QC (external vendors off site data)	Non major for Off-site assessment
Forbidden concomitant medication	Any contrast agent (MRI or CT) administered during the course of the trial or within 24 hours after the trial product administration	Clinical Database	Non major for both assessments
IMP deviation	Patient does not receive the IMP allocated by randomization on the IRT system and IMP is different from the one allocated	IWRS Database	Major for both assessments
	Patient does not receive the IMP allocated by	IWRS Database	Non major for both assessments

CONFIDENTIAL	STATISTICAL ANALYSIS PLAN N° GDX-44-016 VERSION N° 4.0 (REF I011622)	F015830-03 Page 20 / 35
--------------	--	----------------------------

Categorisation of the deviation	Protocol Deviation Coded Term	Source	Status
	randomization on the IRT system and IMP received is the same from the one allocated		
	The IMPs volume actually administered is different from the theoretical one from 5 to 10 % (relative difference)	Clinical database, IWRS database	Non major for both assessments
	The IMPs volume actually administered is different from the theoretical one by more than 10 % (relative difference)	Clinical database, IWRS database	Major for both assessments
	Injection rate <4 mL/sec	Clinical database	Major for both assessments
	The volume of saline flush injected is different from 20 mL	Clinical database	Non major for both assessments
	Temperature excursion for IMP	Monitoring	Non major for both assessments
	IMP management not appropriate	Monitoring	Non major for both assessments
Missing data	Blood sampling for Serum creatinine result and EGFR calculation is not performed at screening	Clinical Database	Non major for both assessments
	Pre-injection Axial 3D T1 weighted GRE sequence performed is not performed	Clinical Database	Non major for both assessments
	Pre-injection Axial 2D T2 weighted T(F)SE sequence performed is not performed	Clinical Database	Non major for both assessments
	Pre-injection Axial 2D Flair sequence performed is not performed	Clinical Database	Non major for both assessments
	Post-injection Axial DSC T2* perfusion sequence is not performed	Clinical Database	Major for both assessments
	Post-injection Axial 3D T1 weighted GRE sequence is not performed	Clinical Database	Non major for both assessments
Non respect of study's schedule and procedures	Grade collected at randomization is not the same as the grade collected in the e-CRF	Clinical database, IWRS database	Major for both assessments

CONFIDENTIAL	STATISTICAL ANALYSIS PLAN N° GDX-44-016 VERSION N° 4.0 (REF I011622)	F015830-03 Page 21 / 35
--------------	--	----------------------------

Categorisation of the deviation	Protocol Deviation Coded Term	Source	Status
	For women of childbearing potential, pregnancy test positive or not performed within 1 day before IMP administered	Clinical Database	Non major for both assessments
	eGFR assessment performed more than 7 days before the IMP administration	Clinical Database	Non major for both assessments
	The patient complete the study and the Safety visit (V3) is not performed	Clinical Database	Non major for both assessments
	Safety visit (V3) performed more than 1 day compared to V2	Clinical Database	Non major for both assessments
GCP deviation	Deviations related to ICF management process	Monitoring	Non major for both assessments
	Source document management not appropriate	Monitoring	Non major for both assessments
	SAE management not appropriate	Monitoring	Non major for both assessments
	Personal data breach	Monitoring	Non major for both assessments
	Other GCP deviations	Monitoring	Non major for both assessments

Patients presenting at least one protocol deviation with a status major will be excluded from the PPS (Off-site PPS and / or On-site PPS).

Frequency and percentages of patients with protocol deviations will be presented breaking down by status (major/non major). A listing of all protocol deviations will also be provided in CSR appendix 16.2.3 and major protocol deviations will be flagged.

